## 8.3 Endpoints

### 8.3.1 Primary Endpoint(s)

The incidence of DLTs is the primary safety endpoint during the DLT evaluation phase.

In terms of efficacy, the primary endpoint for SCLC is investigator assessed ORR for the Dose Evaluation Phase and the single arm Dose Expansion Phase. If the randomized Phase 2 study in SCLC subjects is triggered, an IRRC will perform blinded independent review of the imaging per RECIST 1.1 criteria for the assessment of ORR. The ORR is defined as the number of subjects with a best overall response (BOR) of complete response (CR) or partial response (PR) divided by the number of treated subjects (the number of randomized subjects for the randomized Phase 2 study with comparative arm). The BOR is defined as the best response designation, as determined by the investigator, recorded between the first dosing date (randomization date for the randomized Phase 2 study with comparative arm) and the date of objectively documented progression per RECIST 1.1 or the date of subsequent anti-cancer therapy, whichever occurs first. CR or PR determinations included in the BOR assessment must be confirmed by a second scan no less than 4 weeks after the criteria for response are first met. For subjects without documented progression or subsequent therapy, all available response designations will contribute to the BOR assessment. For subjects who continue treatment beyond

progression, the BOR should be determined based on response designations recorded up to the time of the initial RECIST 1.1-defined progression.

For PAC, the primary endpoint is investigator assessed ORR for the Dose Evaluation Phase and the single arm Dose Expansion Phase. Overall survival (OS) is the primary endpoint for the randomized two-arm Phase 2 study. The ORR is defined as above and OS is defined as the time between the randomization date and the date of death due to any cause. A subject who has not died will be censored at the last known alive date.

### **8.3.2 Secondary Endpoint(s)**

Safety and tolerability will be analyzed through the incidence of DLTs, adverse events, serious adverse events, and specific laboratory abnormalities (worst grade). Toxicities will be graded using the NCI CTCAE version 4.0.

PFS is defined as the time from first dosing date (randomization date for the randomized Phase 2 study with comparative arm) to the date of the first documented tumor progression, as determined by the investigator (per RECIST 1.1), or death due to any cause, whichever occurs first. Subjects who die without a reported prior progression will be considered to have progressed on the date of their death. Subjects who did not progress or die will be censored on the date of their last evaluable tumor assessment. Subjects who did not have any on-study tumor assessments and did not die will be censored on the date of their first dosing date (randomization date for the randomized Phase 2 study with comparative arm). Subjects who started anti-cancer therapy without a prior reported progression will be censored on the date of their last evaluable tumor assessment prior to the initiation of subsequent anti-cancer therapy.

### **8.3.3 Exploratory Endpoint(s)**

[Redacted]

[Redacted]

[Redacted]

[Redacted]

## **8.4 Analyses**

All analyses will be presented separately by tumor type.

### **8.4.1 Demographics and Baseline Characteristics**

Demographic and baseline characteristics will be summarized using descriptive statistics.

### **8.4.2 Efficacy Analyses**

For the Dose Evaluation Phase, efficacy analyses will be summarized using the All Dose Evaluation Randomized Treated Subjects by randomized cohort (primary population). Additionally, analyses including all efficacy data collected during that Phase using the All Treated Subjects population will be provided by regimen. Analyses will be presented as-treated.

If the form of the Expansion Phase is a Simon 2-stage like design, efficacy analyses will be summarized for the regimen recommended for the Dose Expansion Phase, pooling data from the related randomized cohort from the All Dose Evaluation Randomized Treated Subjects during Stage 1 with the Stage 2 data (primary population). Additionally, analyses using the All Treated Subjects and including all efficacy data collected for that regimen during the Dose Evaluation and the Dose Expansion Phases will be provided. Analyses will be presented as-treated.

If a randomized Phase 2 study with comparative arm is initiated, efficacy analyses will be presented separately by treatment arm using the All Expansion Phase Randomized Subjects. Analyses will be presented as-randomized.

#### **8.4.2.1 Primary Endpoint Methods**

ORR will be summarized by a binomial response rate and corresponding two-sided 90% exact CI using the Clopper and Pearson method. If a randomized Phase 2 study with comparative arm is initiated, ORR will be compared between the treatment arms using a one-sided alpha level of 0.10 with Cochran-Mantel-Haenszel (CMH) test stratified by the stratification factors defined for each tumor type. A two-sided, 80% CI for the difference in response rates will also be computed, adjusting for the stratification factors.

The primary analysis of OS as primary endpoint for PAC will be a comparison of the OS of subjects randomized to ulocuplumab plus nivolumab to that of subjects randomized to the investigator's choice chemotherapy using a one-sided alpha level of 0.10 log-rank test stratified by the stratification factors defined for each tumor type. The hazard ratio and associated two-sided 80% confidence interval will be computed using an univariate Cox proportional hazards model with treatment as the sole covariate. Further analyses of OS will be summarized descriptively using Kaplan-Meier methodology. Median values of OS, along with two-sided 95% CIs using the Brookmeyer and Crowley method considering a log-log transformation, will be calculated. OS rates at 3, 6, 9, 12, 18 and 24 months will be estimated as well as associated two-sided 95% CIs considering a log-log transformation.

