**Table 3.1.1-1: Dose Levels for Ulocuplumab and Nivolumab**

Dose Level	Ulocuplumab	Nivolumab
DL-1	200 mg weekly	3 mg/kg every 2 weeks
DL1	400 mg weekly	3 mg/kg every 2 weeks
DL2	800 mg weekly	3 mg/kg every 2 weeks
DL3A	1600 mg weekly	3 mg/kg every 2 weeks

DL3B	1600 mg every 2 weeks	3 mg/kg every 2 weeks
------	-----------------------	-----------------------

Depending on the number of DLT observed during the DLT evaluation period, escalation or de-escalation of ulocuplumab may be warranted. Dose escalation/de-escalation at the 800 mg weekly and 1600 mg weekly ulocuplumab dose levels will occur independently for each tumor type. No dose modification of nivolumab will be allowed in this study.

- If the toxicity at DL1 and DL2 and DL3A are acceptable, enrollment will proceed with three randomized cohorts (DL2, DL3A, and DL3B) to complete Stage 1
- If the toxicity at DL3A is unacceptable, enrollment will proceed at DL2 to complete Stage 1
- If the toxicity at DL2 is unacceptable, enrollment will proceed at DL1 to complete Stage 1
- If the toxicity at DL1 is unacceptable, a new DLT evaluation period will proceed at DL-1
- If the toxicity of DL-1 is unacceptable, enrollment will stop for that tumor type
- If the toxicity at DL-1 is acceptable, enrollment will proceed at DL-1 to complete Stage 1 at a single dose level

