#### **PAC**

A randomized Phase 2 study with comparative arm in PAC will compare the recommended dose of ulocuplumab combined with nivolumab versus Investigator’s Choice 2L chemotherapy. The main goal of this comparison will be to determine if ulocuplumab plus nivolumab combination therapy is superior to 2L chemotherapy. The primary endpoint of this study will be OS. Safety,

tolerability and PFS will be considered as secondary endpoints. For PAC, a randomized Phase 2 study would require an additional 125 subjects per arm (ie. 250 for the two arms). [REDACTED]. The PAC subjects included in the Dose Evaluation Phase will not be considered in the analysis of the randomized Phase 2 study. Investigator's choice chemotherapy options in this study are based on NCCN guidelines for PAC and include the following.

- Subjects that have failed FOLFIRINOX or other fluoropyrimidine based regimens can consider gemcitabine-based therapies for this study
- Subjects that have failed gemcitabine based regimens can consider fluoropyrimidine-based regimens for this study

Stratification factors will be used for this portion of the study and will include performance status (ECOG 0 vs 1) and type of chemotherapy used in the first line setting (fluoropyrimidine-containing vs gemcitabine-containing regimens). For additional statistical considerations for the randomized Phase 2 study with comparative arm in PAC subjects, please see [Section 8](#).

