##### **2. Target Population**

a) Subjects with pathologically confirmed metastatic disease of the following tumor types:

i) Subjects with histologically confirmed pancreatic ductal adenocarcinoma (PDAC) who must meet the following:

(1) Subjects must have had progression, refractory disease or best response of stable disease during or after at least 1 chemotherapy regimen for the treatment of metastatic (Stage IV) disease.

Note: For DLT evaluation phase only, subjects may have had progression, refractory disease or best response of stable disease during or after at least 1 chemotherapy regimen for the treatment of locally advanced or metastatic (Stage IV) disease.

AND

- (2) Subjects must not have clinically relevant ascites at baseline, such as ascites in need of paracentesis.
- ii) Subjects with histologically or cytologically confirmed SCLC. Subjects must have progression or refractory disease to most recent therapy. Subjects must have had at least 1 platinum based chemotherapy regimen for the treatment of limited or extensive stage disease.
- b) Subjects must have measurable disease by CT or MRI per RECIST 1.1 criteria (radiographic tumor assessment must be performed within 28 days prior to first dose).
- c) Eastern Cooperative Oncology Group (ECOG) performance status of 0 or 1.
- d) All baseline laboratory requirements will be assessed and should be obtained within 14 days of first dose. Screening laboratory values must meet the following criteria:
- WBCs  $\geq 2000/\mu\text{L}$
  - Neutrophils  $\geq 1500/\mu\text{L}$
  - Platelets  $\geq 120 \times 10^3/\mu\text{L}$
  - Hemoglobin  $\geq 9.0 \text{ g/dL}$
  - Creatinine serum creatinine  $\leq 1.5 \times \text{ULN}$  or creatinine clearance (CrCl)  $\geq 40 \text{ mL/minute}$  (using Cockcroft/Gault formula)
  - AST and ALT levels  $\leq 3 \times \text{ULN}$  or  $\leq 5 \times \text{ULN}$  if liver metastases are present
  - Total Bilirubin  $\leq 1.5 \times \text{ULN}$  (except subjects with Gilbert Syndrome who can have total bilirubin  $< 3.0 \text{ mg/dL}$ )
  - Albumin  $\geq 3 \text{ g/dL}$
  - Lipase  $\leq 1.5 \text{ ULN}$ . Subjects with Lipase  $> 1.5 \text{ ULN}$  may enroll if there are neither clinical nor radiographic signs of a pancreatitis.
  - Amylase  $\leq 1.5 \text{ ULN}$ . Subjects with Amylase  $> 1.5 \text{ ULN}$  may enroll if there are neither clinical nor radiographic signs of a pancreatitis.

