- If an open label randomized Phase 2 study with comparative arm is initiated (1:1 ratio), the primary measurement for efficacy will be OS. A one-sided alpha level of 0.10 log-rank test will be used to compare the OS of subjects randomized to the combination arm of ulocuplumab plus nivolumab to that of subjects randomized to the investigator's choice chemotherapy arm. In order for the test to have at least 80% power to reject the null hypothesis of no difference in OS among treatment arms when the hazard ratio of the experimental arm to the control arm is 0.75, the study will require 218 events (deaths) to complete. The analysis of OS will take place when the following two conditions have been met: 218 events have been observed and all subjects have been on study for at least 6 months. The requirement that subjects be on study for at least 6 months is meant to ensure adequate follow-up. A total of 250 subjects are to be randomized. Assuming an accrual rate of 20 subjects per month, the accrual will last approximately 13 months. Assuming exponentially distributed OS and median OS times in the control and experimental arms of

4.5 months and 6.0 months, respectively, it is expected that the requisite number of events (deaths) will occur approximately 10 months after all subjects have been randomized.

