 - ◆ If the Dose Expansion Phase is of the form of a Randomized Phase 2 design, a summary of the Dose Expansion Phase will take place, separately from the Randomized data.

- Dose Expansion Phase:
 - 2-stage design
 - ◆ An IA will be conducted when all subjects have a minimum of 3 months of treatment or discontinued prematurely. The objectives of this IA will be similar to item 1) and 2) of the Dose Evaluation Phase IA objectives.
 - ◆ The final analysis will take place when all subjects will have discontinued the study.
 - Randomized Phase 2
 - ◆ IAs will be conducted on a regular basis for the interim monitoring as specified in the Data Monitoring Committee (DMC) charter.
 - ◆ The final analysis will take place when all subjects will have discontinued the study.

At the time of finalizing this SAP, it is known that subjects reported more than 2 DLTs in the “ulocuplumab 400mg weekly combined with nivolumab” cohort (DL1, in PAC subjects). Therefore, and according to protocol, the DL-1 cohort (ulocuplumab 200mg weekly combined with nivolumab) has been initiated. Following this and, considering the current study design, there will be no randomization during the Dose Evaluation phase and no use of the DL3B regimen: “ulocuplumab at 1600mg every 2 weeks combined with nivolumab”. The current version of this SAP is using this information and does not consider that randomization nor the DL3B regimen while describing the planned analyses. Also, as no ulocuplumab dose reduction were reported for the DL1 cohort and as the DL-1 cohort does not allow dose reduction no analysis related to ulocuplumab dose reduction will be planned.

Also, to streamline the document, any reference to the analysis of the potential “Randomized Phase 2” part of the study are not included at this time and may be added at a later time if warranted.

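### PAC overall survival: the primary test is stratified, but the hazard ratio and its 80% interval come from a Cox model that names no strata

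*Protocol*

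**What the plan says.** Protocol 3.1.3, under PAC, sets two binary factors for the randomised part: "Stratification factors will be used for this portion of the study and will include performance status (ECOG 0 vs 1) and type of chemotherapy" given first-line (fluoropyrimidine- or gemcitabine-containing). That makes four strata.

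Protocol 8.4.2.1 analyses overall survival with a "one-sided alpha level of 0.10 log-rank test stratified by the stratification factors defined for each tumor type". The synopsis describes the same test. The next sentence of 8.4.2.1 says that the hazard ratio and a two-sided 80% interval will be "computed using an univariate Cox proportional hazards model with treatment as the sole covariate".

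For response rate, the same section pairs a stratified Cochran-Mantel-Haenszel test with a two-sided interval that does carry the strata: "80% CI for the difference in response rates will also be computed, adjusting for the stratification factors".

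Nothing else settles the point. The synopsis names no model for the hazard ratio. SAP 7.5.2 is Kaplan-Meier only, and SAP section 2 leaves the randomised Phase 2 analyses to a possible later version.

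**The concern.** An 80% two-sided interval is the natural companion of a one-sided 0.10 test, so readers will expect the interval to exclude 1 when the test is significant. That correspondence is close only if both use the same strata. A stratified log-rank test relates to a hazard ratio within strata. An unstratified Cox model estimates a hazard ratio between whole arms. The two quantities differ when the strata are prognostic and treatment has an effect.

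This is a difference of estimand, not a bias. At stake is whether the primary p-value and the effect estimate printed beside it tell the same story, and whether two analysts would program the same model from this sentence. The choice is better fixed before survival data from an open-label study are seen.

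**Working it through.** **Planning figure.** Inputs from Protocol 8.1.2: hazard ratio 0.75, one-sided alpha 0.10, 80% power, 1:1 allocation. By Schoenfeld's formula:

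deaths = 4 × (z₀.₉₀ + z₀.₈₀)² / (ln 0.75)² = 4 × (1.2816 + 0.8416)² / 0.28768² ≈ 217.9, rounded up to 218.

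This reproduces the protocol's 218 (power at 218 deaths: 80.0%). With 218 deaths, the standard error of the log hazard ratio is about 2/√218 = 0.135. The approximate significance cut-off is exp(−1.2816 × 0.135) = 0.841. An observed 0.75 has an 80% interval of about 0.630 to 0.892. The protocol states "Assuming exponentially distributed OS and median OS times in the control and experimental arms of" 4.5 and 6.0 months, and 4.5/6.0 = 0.75, so the planning hazard ratio is itself an arm-level ratio.

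**Simulation set-up.** From the documents: 250 randomised, accrual of 20 per month (250/20 = 12.5 months), a control median of 4.5 months, and analysis at the later of the 218th death and 6 months after the last randomisation. Assumed, because the documents give no values: ECOG 1 in 60%, one first-line category in 50%, permuted blocks of 4 within strata, exponential survival within strata, and the prognostic hazard ratios listed below. There were 10,000 trials per scenario. With no prognostic effect, the 218th death came on average 10.1 months after accrual ended, which matches the protocol's 10 months.

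**Definition of disagreement.** The stratified one-sided 0.10 log-rank decision differs from whether the upper 80% Wald limit of the unstratified Cox model lies below 1.

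**Results at a within-stratum hazard ratio of 0.75:**

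| Assumed ECOG / first-line HR | Mean HR, unstratified vs stratified | Disagreement | Test significant, interval includes 1 | Reverse |
|---|---|---|---|---|
| 1 / 1 | 0.749 vs 0.749 | 3.5% | 1.33% | 2.14% |
| 1.1 / 1.1 | 0.749 vs 0.749 | 3.8% | 1.67% | 2.15% |
| 1.25 / 1.1 | 0.752 vs 0.750 | 4.1% | 1.96% | 2.10% |
| 1.25 / 1.3 | 0.754 vs 0.749 | 4.3% | 2.45% | 1.85% |
| 1.5 / 1.3 | 0.757 vs 0.749 | 5.0% | 2.93% | 2.08% |
| 2.0 / 1.3 | 0.768 vs 0.749 | 7.5% | 5.21% | 2.31% |
| 2.5 / 1.3 | 0.780 vs 0.750 | 10.7% | 8.48% | 2.18% |

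The Monte Carlo standard error of the disagreement rate is 0.14 to 0.31 points across the scenarios run.

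- Excess over the no-effect row: 0.4 to 0.8 points in the three mild cases, then 1.5, 4.1 and 7.2 points at ECOG 1.5, 2.0 and 2.5.
- Mean shift in the log hazard ratio: about 0.02 standard errors at 1.25/1.1, and 0.08, 0.18 and 0.28 at ECOG 1.5, 2.0 and 2.5.
- In single trials the unstratified estimate is still the lower of the two in 47% (1.25/1.1), falling to 22% (ECOG 2.5).
- True hazard ratio of 1: no shift, and 2.0% to 4.3% disagreement.
- Cox model stratified by the same factors: at most 0.07% disagreement in every scenario.

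A separately coded simulation (3,000 trials per scenario) at hazard ratio 0.75 gave 3.4% with no prognostic effect, 4.8% at 1.5/1.2 and 8.2% at 2.0/1.5, again with at most 0.07% for the stratified model.

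**Chance that this part opens.** It needs at least 6 responders among 21 (Protocol 3.1.2 and 8.5). The exact binomial probability is 0.00044 at a true response rate of 5% and 0.231 at 20%.

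**The case against.** The strongest reply is that there is no contradiction. A Cox model can be stratified and still have treatment as its only covariate. Alternatively, the authors, who wrote the strata into the response-rate interval, may have chosen an arm-level hazard ratio on purpose, and that matches the arm-level planning value. When 0.75 is taken as the arm-level value (within-stratum 0.73, ECOG 2.0), the unstratified model returns 0.748, with 6.3% disagreement. All of this stands. It makes the sentence ambiguous rather than wrong, and the unstratified estimate legitimate.

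The numbers are also small. The first mild case exceeds the no-effect baseline by only 0.35 points (3.82% − 3.47%), about 1.3 Monte Carlo standard errors. In the two mildest prognostic cases the commoner disagreement is the less troubling one. The larger figures need an assumed ECOG hazard ratio of 2.0 or more in a population restricted to "Eastern Cooperative Oncology Group (ECOG) performance status of 0 or 1". That stands too, and those rows show only the upper end of a range.

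The setting is remote. SAP section 2 reports that "it is known that subjects reported more than 2 DLTs in the" 400 mg weekly cohort, in pancreatic patients, and that the 200 mg level was opened. Protocol 3.1.1 adds: "If the toxicity of DL-1 is unacceptable, enrollment will stop for that tumor type". The SAP has openly deferred the randomised analyses, so its silence is not a fault.

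Finally, on the plain reading, stratifying the model changes it rather than merely clarifying it. That is fair. None of this, however, tells an analyst which model to fit, and 8.4.2.1 remains the only text that specifies one.

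**Conclusion.** The concern holds as a low-severity point of reporting consistency. Read plainly, the protocol pairs a stratified test with an unstratified hazard ratio and interval, and no other text resolves it. Disagreement is about 4% with non-prognostic or weakly prognostic strata, and a significant test beside an interval that includes 1 is not then the commoner pattern. That pattern becomes clearly the commoner one only from an assumed ECOG hazard ratio of about 1.5 (with 1.3 for first-line regimen), where total disagreement is 5.0%, rising to 10.7% at 2.5. These figures rest on assumed prognostic effects and stratum shares.

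The primary p-value, type I error, power and 218 deaths are untouched, and no decision rule uses the interval. The point matters only if the randomised pancreatic part opens.

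**What to change.** Reword the sentence in Protocol 8.4.2.1 to say that the overall survival hazard ratio and its two-sided 80% interval come from a Cox model with treatment as the only covariate, stratified by the log-rank factors (ECOG status and first-line regimen type). Keep the unstratified model as a sensitivity analysis, labelled as the arm-level hazard ratio. If the randomised part is added to the SAP, put the same sentence there.

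If the sponsor prefers the arm-level estimate as the main one, saying so explicitly would remove the ambiguity but leave the mismatch with the test.

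The cost is one sentence in the protocol, which can go into a later revision, and the same sentence in the SAP. The factors are already recorded for randomisation, so no data, patients or events are added.

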#### **8.4.2.2 Secondary Endpoint Methods**

PFS as a secondary endpoint will be descriptively summarized as for OS above. PFS rates at 3, 6, 9, 12, and 18 months will be estimated as well as associated two-sided 95% CIs considering a log-log transformation.

#### **8.4.2.3 Exploratory Endpoint Methods**

[REDACTED]

#### **8.4.3 Safety Analyses**

Except where indicated, safety analyses will be using the All Treated Subjects population and will be presented as-treated.

During the DLT evaluation Phase, the primary analysis will consist of the incidence of DLTs among DLT-evaluable Subjects but all available safety and tolerability data will be used to assess the safety of the regimens.

For the Dose Evaluation Phase, safety analyses will be summarized by randomized cohort. Additionally, analyses including all safety data collected during that Phase will be provided by regimen.

If the form of the Expansion Phase, is a Simon 2-stage like design, safety analyses will be summarized for the regimen recommended for the Dose Expansion, pooling data from both stages of the study. Additionally, analyses including all safety data collected for that regimen during the Dose Evaluation and the Dose Expansion Phases will be provided.

If a randomized Phase 2 study with comparative arm is initiated, safety analyses will be presented separately by treatment arm.

Events (AEs or laboratory) will be counted as on-study if the event occurred within 100 days of the last dose of ulocuplumab or within 100 days of the last dose of nivolumab, whichever is later. All on-study AEs, treatment-related AEs, SAEs, treatment-related SAEs, AEs leading to discontinuation and treatment-related AEs leading to discontinuation will be tabulated (All Grades and Grade 3-4) using worst grade per NCI CTCAE v 4.0 criteria by system organ class and preferred term. On-study laboratory abnormalities including hematology, chemistry,

liver function, and renal function will be summarized (All Grades and Grade 3-4) using worst grade NCI CTCAE v 4.0 criteria.

[REDACTED]

[REDACTED]

[REDACTED]

[REDACTED]

[REDACTED]

[REDACTED]

[REDACTED]

Baseline and change from baseline in EORTC-QLQ-C30 global health status/QoL composite scale data and the remaining EORTC QLQ-C30 scale data will be summarized by time point using descriptive statistics for each cohort (N, mean, standard deviation, median, first and third quartiles, minimum, maximum). In addition, the percentage of subjects demonstrating a clinically meaningful change (defined as a 10 point change from baseline) will be presented for each scale at each subsequent time point. Percentages will be based on number of subjects assessed at assessment time point.

